3.2.2 Exclusion Criteria

A patient who meets any of the following exclusion criteria at screening and/or baseline is excluded from participation in this trial:

1. Is unable or unwilling to participate in all scheduled visits and perform all protocol-mandated assessments.
2. Has a known or suspected hypersensitivity to ilofotase alfa or any components of the formulation used.
3. Body weight < 40 kilogram and > 120 kilogram.
4. Patient has a history of clinically significant abnormalities or of any illness that, in the opinion of the trial investigator, might confound the results of the trial or pose an additional risk to the patient by their participation in the trial.
5. NSAID use in the past 2 weeks.
6. Use of corticosteroids in the past 4 weeks.
7. Compounds intended to interfere with bone metabolism (e.g. Denosumab, Teriparatide, Romosozumab, Raloxifene) in the past 3 months.
8. Use of bisphosphonates in the past 2 years.
9. Participation in a drug trial within 60 days, or five times the half-life of the drug, whichever is longer, prior to administration of ilofotase alfa.
10. Use of asfotase alfa in the previous 3 months. Patients will not be withheld from approved asfotase alfa if medically indicated.
11. A patient who is currently pregnant or lactating.
12. Use of Supplements including Vitamin B6.

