- Women of Child Bearing Potential must agree to use adequate and effective contraception means (criteria CTFG, 2020) for the period between trial drug administration and 14 days thereafter.
- Post-menopausal females not requiring hormonal contraception are defined as: no menses for 12 months without an alternative cause, and follicle stimulating hormone level must be used to confirm post-menopausal state in women not using hormonal contraception or hormonal replacement therapy (CTFG, 2020).
- Male subjects must agree to wear a condom during sexual intercourse and in case their partner is of child bearing potential they must agree to use adequate and effective contraception means (criteria CTFG, 2020) for the period between trial drug administration and 14 days thereafter.

Exclusion criteria

A patient who meets any of the following exclusion criteria at screening and/or baseline is excluded from participation in this trial:

1. Is unable or unwilling to participate in all scheduled visits and perform all protocol-mandated assessments.
2. Has a known or suspected hypersensitivity to ilofotase alfa or any components of the formulation used.
3. Body weight < 40 kilogram and > 120 kilogram.
4. Patient has a history of clinically significant abnormalities or of any illness that, in the opinion of the trial investigator, might confound the results of the trial or pose an additional risk to the patient by their participation in the trial.
5. NSAID use in the past 2 weeks.
6. Use of corticosteroids in the past 4 weeks.
7. Use of compounds intended to interfere with bone metabolism (e.g. Denosumab, Teriparatide, Romosozumab, Raloxifene) in the past 3 months.
8. Use of bisphosphonates in the past 2 years.
9. Participation in a drug trial within 60 days, or five times the half-life of the drug, whichever is longer, prior to administration of ilofotase alfa.
10. Use of asfotase alfa in the previous 3 months. Patients will not be withheld from approved asfotase alfa if medically indicated.
11. A patient who is currently pregnant or lactating.
12. Use of supplements including Vitamin B6.

Trial Drug, Dosage, and Route of Administration

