⁶ PK sampling on day 1 will include baseline, end of infusion, 2, 4 and 8 hours post infusion

⁷ Samples to be drawn in the morning while fasting, for PPi and PLP (both Vitamers)

⁸ Samples at baseline, 2, 4 and 8 hours after start dosing will be in non-fasted patients

⁹ Immediately consecutive sampling (second morning urine) of urine and blood for PEA, creatinine, phosphorus, and calcium concentrations. To assess phosphate reabsorption (TmP/GFR and TRP) kidney function and Ca/creatinine ratio

¹⁰ 25 OH Vitamin D, ALP Isoenzyme, c-Terminal iFGF-23, PTH, CTX, PINP, Osteocalcin, PEA Urine (absolute und relative to sCreat), Purines and other biomarkers

¹¹ This includes SAE reporting

¹⁰ Baseline is defined as measurements taken on day -2, day -1 and day 1. Measurements taken on day 1 must be taken at any time up to immediately before randomization to be considered as baseline measurements. Measurements taken at or after randomization are not considered baseline measurements. Note that there is no day 0.

TABLE OF CONTENTS

1. INTRODUCTION	12
1.1 Background	12
1.1.1 Alkaline Phosphatase and Hypophosphatasia	12
1.1.2 Recombinant Human Alkaline Phosphatase (ilofotase alfa)	12
1.1.3 Clinical Studies with Recombinant Human Alkaline Phosphatase (ilofotase alfa)	12
1.2 Rationale.....	12
Risk - Benefit	13
2. OBJECTIVES	13
3. INVESTIGATIONAL PLAN.....	13
3.1 Trial Design and Plan.....	13
3.1.1 Trial design.....	13
3.1.2 Screening and Informed consent.....	13
3.1.3 Treatment Period.....	13
3.1.4 Follow-up	13
3.1.5 Discussion Trial Design.....	13
3.2 Selection of Trial Population.....	14
3.2.1 Inclusion Criteria	14
3.2.2 Exclusion Criteria	14
3.2.3 Removal of Patients from Therapy or Assessment.....	15
3.3 Treatments.....	15
3.3.1 Treatments Administered	15
3.3.2 Identity of Investigational Product	15
3.3.3 Trial Drug Preparation	15
3.3.4 Trial Drug Administration.....	16
3.3.5 Trial Drug Handling and Storage	16
3.3.6 Drug accountability.....	16
3.3.7 Drug Storage	16
3.3.8 Method of Assigning Patients to Treatment Groups	16
3.3.9 Meals during the Trial	17
3.3.10 Blinding	17
3.3.11 Previous / Concomitant Medication and Other Restrictions during the Trial	17
3.3.12 Treatment Compliance	17
3.3.13 Prohibited Medication During the Trial (including the screening period)	17
3.3.14 Female subjects	17
3.4 Sample collection.....	18
3.4.1 Primary endpoint samples	18
3.4.1.1 PPi.....	18
3.4.1.2 PLP.....	18
3.4.2 Exploratory assessments	18

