3.1.2 Screening and Informed consent

Patients will report for the eligibility screening according to the inclusion and exclusion criteria defined in Section 3.2 within 6 weeks prior to the first drug administration.

Patients will voluntarily sign the trial specific Informed Consent Form (ICF) prior to any trial specific screening procedures being performed. The written informed consent will be obtained for all patients, regardless of their eligibility for the trial; the signed ICFs will be retained and archived at the trial center and another copy will be provided to the patient.

Eligibility screening will consist of assessments as presented in the Schedule of assessments Table 1.

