3.3.13 Prohibited Medication During the Trial (including the screening period)

1. NSAIDs
2. Corticosteroids
3. Compounds intended to interfere with bone metabolism (e.g. Denosumab, Teriparatide, Romosozumab, Raloxifene).
4. Bisphosphonates
5. Supplements including Vitamin B6
6. Asfotase alfa

If there is a clinical indication to start any of these above medication, the subject should be withdrawn from the trial. Subjects who initiate any of the medication mention above during the trial period will be considered dropouts.

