3.4.1 Primary endpoint samples

All samples to be obtained while fasting in the morning. There will be 3 samples obtained to determine baseline (day -2, day -1, and day 1 before randomization and dosing). There will be 12 samples obtained to determine changes in response to treatment (3 samples on day 1 (*2, 4, and 8 hours after start dosing*), and daily samples from day 2 until day 10.

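### Exclusion 12 sets no time window for vitamin B6 supplements, so a patient who has just stopped them may enter the PLP baseline with a level that is still falling

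*Protocol*

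**What the plan says.** The criterion appears twice without a time period: "Use of supplements including Vitamin B6" in the synopsis and "Use of Supplements including Vitamin B6" in section 3.2.2. The lead-in to the list is "A patient who meets any of the following exclusion criteria at screening and/or baseline is excluded from participation in this trial".

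The related rules are these:

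- Section 3.1.2 places screening "within 6 weeks prior to the first drug administration". This is a maximum; no minimum is given. Table 1 puts consent and the first eligibility check in the day -2 column.
- Section 3.3.13 is headed "Prohibited Medication During the Trial (including the screening period" and lists B6 supplements. Its dropout rule is "Subjects who initiate any of the medication mention above during the trial period will be considered dropouts". The synopsis version of the list names only the trial period, which the synopsis starts with the run-in on day -2.
- On the baseline, section 3.4.1 says "There will be 3 samples obtained to determine baseline (day -2, day -1, and day 1 before randomization and dosing". Section 3.6.2.1 takes the median of the pre-randomization values and summarizes PLP as change, percentage change and maximum change from it.
- Section 3.1.1 gives both arms active drug.
- Table 1, footnote 7, treats PLP as a vitamer: "Samples to be drawn in the morning while fasting, for PPi and PLP (both Vitamers".

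**The concern.** By banning B6 supplements the protocol implies that they can disturb PLP, one of the two primary markers. It gives a look-back for NSAIDs, corticosteroids, bone agents, bisphosphonates, other trial drugs and asfotase alfa, but not for the product closest to a primary endpoint.

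If PLP is raised by a supplement and falls after it is stopped, a patient who stopped a few days before day -2 starts from an inflated and declining baseline. The fall looks like a drug effect. Both arms are treated, so no group shows what PLP would have done without the drug. The trial is meant to inform a possible Phase 2/3 trial on whether the drug can normalize PLP, and that question rests on the within-arm change.

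**Working it through.** **1. Look-backs side by side (section 3.2.2)**

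| Exclusion | Look-back |
|---|---|
| 5 NSAIDs | 2 weeks |
| 6 corticosteroids | 4 weeks |
| 7 bone-metabolism compounds | 3 months |
| 8 bisphosphonates | 2 years |
| 9 other drug trials | 60 days or five half-lives, whichever is longer |
| 10 asfotase alfa | 3 months |
| 12 supplements including B6 | none |

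**2. Guaranteed B6-free time before the first baseline PLP sample**

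Table 1 notes that there is no day 0, so day -2 is 2 days before dosing. With use read as current use, and the section 3.3.13 ban running from screening:

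guaranteed days = (days from screening to dosing) − 2

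- Screened day -42: 42 − 2 = 40
- Screened day -28: 28 − 2 = 26
- Screened day -14: 14 − 2 = 12
- Screened day -2, as laid out in Table 1: 2 − 2 = 0

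Under the synopsis list, where the ban starts only with the trial period, the guarantee is about 0 whatever the screening date.

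**3. What a drift does to the change from baseline**

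Let PLP fall by d per day without any drug effect; the documents do not give d. For a steady fall, the median of days -2, -1 and 1 is the day -1 value, so the median does not remove the trend. Day k lies k days after day -1, so the change on day k contains k·d:

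- day 1 post-dose samples: about 1d
- day 10: 9 + 1 = 10 days, so 10d
- the three baseline samples span 2 days and show only 2d

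One such patient in an arm of 6 would move that arm's mean day 10 change by 10d / 6 = 1.7d. The 10d and 1.7d are worst cases: they need a constant rate and apply to day 10 only. If the fall slows, they shrink.

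**4. Sensitivity under assumed kinetics**

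This is an illustration only, because the protocol gives neither quantity. Assume that a share e of PLP on supplements is excess, decaying with half-life h, and that w days have passed between the start of the decay and day -2. With t in days from day 1:

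PLP(t) ∝ (1 − e) + e · 0.5^((t + 2 + w)/h)

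Example with h = 10, w = 0, e = 0.25: baseline (t = −1) is 0.75 + 0.25 × 0.933 = 0.9833; day 10 (t = 9) is 0.75 + 0.25 × 0.4665 = 0.8666; change 0.8666/0.9833 − 1 = −11.9%.

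Fall from baseline to day 10 in one affected patient, no drug effect, e from 25% to 50%:

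| B6-free days before day -2 | h = 10 days | h from 2 to 30 days |
|---|---|---|
| 0 | 12% to 24% | 5% to 40% |
| 14 | 5% to 13% | 0% to 13% |
| 28 | 2% to 6% | 0% to 8% |
| 40 | 1% to 3% | 0% to 6% |

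The table shows that the washout length could matter. It is not an estimate of the bias in this trial.

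**The case against.** **The wording may not admit recent users.** Exclusion 11, just above, says currently; exclusion 12 does not. An investigator could count use on the day before screening as use and exclude the patient. This stands in part. A reader might infer that dosing someone who took B6 until day -3 is plainly compliant, but that holds only on the current-use reading. Still, a criterion open to both readings can be applied differently from patient to patient.

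**The harm is not quantified.** This stands. The protocol gives no PLP kinetics, no supplement effect and no count of B6 users. A reader might take 10d, or the percentages above, as the expected contamination of the primary summaries. The documents do not support that. Maximum change, and the composite of lowest levels, carry 10d only if the lowest value falls on day 10; if it comes soon after the infusion they carry about 1d.

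**Safeguards exist.** Table 1 records previous and concomitant medication from day -2, there are three pre-dose samples, and levels are listed and graphed daily for at most 12 patients. A marked drift could be noticed, but noticing it does not take it out of the change from baseline. The dropout rule in section 3.3.13 concerns patients who start a product, not those who have just stopped.

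**Randomization protects the dose comparison.** It does so on average. With 6 per arm, if 2 of 12 patients had recently stopped, both would fall in the same arm with probability 5/11 = 0.45. It does nothing for the within-arm change.

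**This is an exploratory pilot.** There is no formal sample size, and section 3.6.2.1 names no test or decision threshold. That limits the consequence. It does not make the missing window a matter for an analysis plan, since eligibility is fixed in the protocol.

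**Conclusion.** The point holds as a gap in an eligibility rule. Exclusion 12 has no look-back and nothing else in the protocol supplies one. If use is read as current use, the guaranteed B6-free time before the first baseline PLP sample can be as short as 0 days and is at most 40, the upper end resting on section 3.3.13. Any PLP decline after stopping would then be mixed into the within-arm and overall PLP change from baseline, without an untreated comparator.

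The direction is plausible, because the protocol itself bans B6. The size cannot be stated from the documents. The exposure is greatest on the later days and small for the samples taken within hours of the infusion. PPi is outside the point, and the dose contrast is unaffected on average. It would go too far to conclude that the PLP results will be biased or that the design fails. This is an inexpensive improvement that should be made.

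**What to change.** In the synopsis and in section 3.2.2, add a window to exclusion 12, for example: within the 4 weeks before day -2. The 4 weeks is an example; the sponsor should justify the length from PLP kinetics.

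Keep the check at both screening and baseline, with the window anchored to day -2. Moving it to baseline alone would drop the existing screening check and could bring in patients who stop B6 in order to join.

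Align the synopsis list of prohibited medication with section 3.3.13, so that the ban covers the screening period in both places.

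The cost is a text amendment, with no added samples or assays. A few recent B6 users would have to wait or be excluded, which matters in a rare disease with up to 12 patients. The present 6-week limit leaves room: screening on day -30 gives 30 − 2 = 28 clear days, so a patient who stopped the day before screening would qualify if screened on any of the 13 days from day -42 to day -30.

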3.2.3 Removal of Patients from Therapy or Assessment

Participation in the trial is strictly voluntary. A patient has the right to withdraw from the trial at any time for any reason.

The Principal Investigator has the right to terminate participation of a patient for any of the following reasons: difficulties in obtaining blood samples, violation of the protocol, severe or serious adverse events (SAEs), or for any other reason relating to the patient's safety or integrity of the trial data.

In the event a patient is withdrawn from the trial, the Sponsor will be informed immediately. If there is a medical reason for withdrawal, the patient will remain under the supervision of the Principal Investigator until satisfactory health has returned.

If the Principal Investigator withdraws a patient for a trial drug related reason (according to the judgement of the Principal Investigator) he/she is considered a dropout.

The site will use best effort to ensure that non-completers and dropouts who have received trial drug complete the follow up assessments.

On withdrawal after dosing and prior to the scheduled Day 10 visit, the assessments of the Day 10 visit should be done accordingly.

3.3 Treatments

3.3.1 Treatments Administered

1-hour iv infusions of 0.8 mg/kg, or 3.2mg/kg ilofotase alfa.

3.3.2 Identity of Investigational Product

Specifications for trial drug administered are summarized in Table 2.

Table 2. Trial Drug Administered

Trial Drug Name	ilofofase alfa
Dosage Formulation	IMP is a clear, colorless to slightly yellow concentrate solution for infusion.
Unit Dose Strength(s)/Dosage Level(s)	Ilofotase alfa has an activity of approximately 5,000 U/mL (units of ALP activity) at 8.0 mg/mL (protein concentration) in an aqueous buffer at a pH of 7.0 containing: 
• 20 mM citrate• 250 mM sorbitol• 2 mM MgCl₂• 50 µM ZnCl₂ The solution will be diluted with sterile sodium chloride 0.9% for injection (isotonic saline), USP/EP or equivalent and administered as an iv infusion to the intended doses. The intended dose will be in a volume of 50 mL.
Route of Administration	Intravenous infusion
Packaging and Labeling	For preparation of the trial drug, vials with 4 mL extractable volume of 8.0 mg/mL ilofotase alfa will be provided and labeled according to EU requirements.
Supplier	Almac Clinical Services Ltd.

3.3.3 Trial Drug Preparation

For preparation of the trial drug, vials with 4 mL extractable volume of 8.0 mg/mL ilofotase alfa will be provided. Prior to administration, the trial drug will be diluted with sterile sodium chloride 0.9% for injection (isotonic saline), USP/EP or equivalent, and administered as an iv infusion using an infusion line with an in-line filter and dosing syringe. The intended dose is 0.8 mg (500 U) per kg of body weight ilofotase alfa or 3.2 mg (2,000 U) per kg of body weight ilofotase alfa. The intended dose will be in a volume of 50 mL.

Reconstituted trial drug can be stored at 2 to 8°C for up to 24 hours or for a maximum of 8 hours at room temperature and protected from light.
Details will be described in the Pharmacy Manual.

3.3.4 Trial Drug Administration

Only patients enrolled and randomized in the trial may receive trial drug. Start and stop time and date of each trial drug administration will be collected in the electronic case report form (eCRF). Trial drug is administered as an iv infusion using an infusion line with an in-line filter and dosing syringe. Infusion will take place at a constant rate of 50 mL/hour for 60 minutes.

3.3.5 Trial Drug Handling and Storage

Receipt and handling of trial drug will be in accordance with procedures at the site. Storage will be in a lockable, monitored storage facility with access limited to authorized staff only. Trial drug vials are to be stored at 2°C to 8°C and protected from light and moisture until preparation for use.
Full details of trial drug packaging, storage, and shipment will be provided in the Pharmacy Manual. Trial drug will be packaged and labeled in accordance with Good Manufacturing Practice (GMP), Good Clinical Practice (GCP) and local requirements.

3.3.6 Drug accountability

Current ICH GCP guidelines require the investigator to ensure that trial drug deliveries from the Sponsor are received by a responsible person (e.g. a pharmacist or delegate), and

- that such deliveries are recorded,
- that trial drug is handled and stored safely and properly,
- that trial drug is only dispensed to trial patients in accordance with the protocol,
- that any unused trial drug is returned to the Sponsor or standard procedures for the alternative disposition of unused trial drug are followed.
- Drug inventory and accountability records for the trial drugs will be kept by the investigator/pharmacist. Trial drug accountability throughout the trial must be documented. The following guidelines are therefore pertinent:
 - i. The investigator agrees not to supply trial drugs to any person except the patients in this trial.
 - ii. The investigator/pharmacist will keep the trial drugs in a pharmacy or other locked and secure storage facility under controlled storage conditions, accessible only to those authorized by the investigator to dispense these test drugs.
 - iii. A trial drug inventory will be maintained by the investigator/pharmacist. The inventory will include details of materials received and a clear record of when they were dispensed and to which patient.
 - iv. At the conclusion or termination of this trial, the investigator/pharmacist agrees to conduct a final drug supply inventory and to record the results of this inventory on the Drug Accountability Record. It must be possible to reconcile delivery records with those of used and returned medication. Any discrepancies must be accounted for. Appropriate forms of deliveries and returns must be signed by the person responsible.
 - v. Unused drug will be locally destroyed according to standard institutional procedures after drug accountability has been conducted by the Sponsor or representative at the end of the trial. If such is not possible, unused drug will be returned to the Sponsor (or its designee).

3.3.7 Drug Storage

Storage at 2°C to 8°C, protected from light and will be indicated on the label.

The clinical supplies storage area at the site must be monitored by the site staff for temperature consistency with the acceptable storage temperature range specified by the Sponsor. Documentation of temperature monitoring should be maintained.

3.3.8 Method of Assigning Patients to Treatment Groups

After obtaining oral and written informed consent, patients will be screened according to the inclusion and exclusion criteria. Patients who have met all eligibility criteria receive a screening number upon inclusion in the trial. Replacement patients, for those patients who fail screening but were not randomized, will receive the screening number of the patient to be replaced, increased by 1000. Patients

who complete screening will be randomized to one of two trial arms, just prior to dosing, and will be given a subject number which will ensure identification throughout the trial.

Patients who dropout or withdraw for any reason before completing all screening evaluations successfully, will be considered as “screening failures”. Such patients will not receive a subject number, but will receive a screening number, only applicable data will be entered in the eCRFs. The Principal Investigator or authorized designee will keep a screening and enrollment log of all patients screened to document patient numbers and passing screening status of enrolled patients into the treatment and patients who fail screening and the reasons for their exclusion.

